Can we enhance the effects of rTMS on motor cortex? A different brain stimulation modality, cervically implanted vagus nerve stimulation (cVNS) can enhance neuroplasticity and facilitate rehabilitation, especially when paired with an intervention such as task-specific training(19, 20). There is a new noninvasive form of this method, transcutaneous auricular vagus nerve stimulation (taVNS). This may also facilitate plasticity and is being investigated in the enhancement of motor learning and recovery in a specific paired fashion. The timing of the paired VNS is critical to the desired neuroplastic changes(21-23), as the behavioral effects of paired therapy disappear when behavior is not intricately synchronized with stimulation. Could pairing taVNS with TMS boost the effects of TMS on cortex, and potentially emerge as a stroke recovery tool? As a first step in this direction, we propose a basic, mechanistic pilot study exploring the use of paired taVNS/TMS to further enhance motor cortex excitability in 24 healthy individuals in a 4 visit, randomized, sham controlled, counterbalanced study.

**Aim 1. Determine the effects of taVNS on motor cortex excitability.** We hypothesize that taVNS alone (sham rTMS + active taVNS) will induce increases in motor cortex excitability (post-stimulation compared to baseline). We believe these changes will be of a lesser magnitude than those of TMS alone (active rTMS + sham taVNS) due to the indirect mechanistic approach of taVNS.

**Aim 2. Determine whether taVNS-paired TMS is more effective at inducing cortical excitability than TMS alone.** We hypothesize that pairing two forms of neuromodulation (active rTMS + active taVNS) will increase TMS-induced cortical excitability in the motor cortex when compared to single modality approaches (active rTMS + sham taVNS; sham rTMS + active taVNS). Furthermore, we believe this increase is timing sensitive, and the paired approach will induce larger TMS-induced cortical excitability compared to unpaired neuromodulation (active taVNS + active taVNS).

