### Study Design

We will enroll 40 healthy individuals into a motor excitability prescreening visit (20Hz rTMS to motor cortex flanked by pre- and post-MEP), and from this prescreen cohort subsequently enroll a total of 24 healthy participants (of whom had increases in motor excitability in the prescreen) into a 4 visit, randomized, sham-controlled trial exploring various forms of neuromodulation on cortical excitability (Figure 1). We will first conduct a baseline measure of cortical excitability using a validated motor evoked potential (MEP) paradigm. Participants will then receive 20 minutes of one of four different stimulation conditions (active TMS, sham TMS, active taVNS, sham taVNS, paired taVNS/TMS, unpaired taVNS/TMS). MEPs will be then recorded immediately after stimulation, and every 10 minutes following for 30 minutes.

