### 11.0 Data Management

Limited demographic and personal health history data will be collected during the phone screen in order to screen out participants with conditions that might confound the research or put them at risk for an

adverse event. All screening data will be kept in a binder in the locked office in the Brain Stimulation Lab as per the requirements of the IRB. Screening data collected from participants who do not qualify for the study will be securely destroyed.

**Power Calculation:** Our proposal utilizes a within-subject design, in which each subject will be their own control. Using the low end of a range of effect sizes (derived from 0.06 partial eta) from prior excitatory TMS/MEP studies (11-13) the proposed study will be sufficiently powered to detect a change in MEP magnitude due to an experimental intervention (paired active/sham rTMS, active/sham taVNS, unpaired taVNS/TMS) using a one-way ANOVA at 80% power and 5% significance level.

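### The only test named and powered is a one-way ANOVA; Aim 2's three pairing comparisons have no test, power or multiplicity rule, and the ANOVA can be significant with no pairing benefit

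*Combined protocol and SAP*

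**What the plan says.** The Power Calculation paragraph in section 11.0 is the only place that names an inferential test. It describes the design ("Our proposal utilizes a within-subject design, in which each subject will be their own control"), gives the effect size ("Using the low end of a range of effect sizes (derived from 0.06 partial eta) from prior excitatory TMS/MEP studies"), and concludes that "the proposed study will be sufficiently powered to detect a change in MEP magnitude due to an experimental intervention", "using a one-way ANOVA at 80% power and 5% significance level". It repeats neither the sample size nor the number of conditions. Those come from Study Design in section 10.0: 24 randomised participants and four conditions.

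Aim 2 in section 1.0 is headed "Determine whether taVNS-paired TMS is more effective at inducing cortical excitability than TMS alone". Its hypotheses are that pairing "will increase TMS-induced cortical excitability in the motor cortex when compared to single modality approaches", meaning TMS alone and taVNS alone, and that "the paired approach will induce larger TMS-induced cortical excitability compared to unpaired neuromodulation (active taVNS + active taVNS"). That makes three comparisons, each with paired stimulation on one side.

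Entrants to the randomised part are those "of whom had increases in motor excitability in the prescreen", which consisted of 20 Hz rTMS. Aim 1 expects taVNS alone to have a smaller effect than TMS alone. Section 4.0 lists MEPs at baseline and at 10-minute steps, with no primary comparison in its text.

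**The concern.** An overall F test asks whether any condition differs from any other. Aim 2 asks whether one particular condition beats three others. The two questions come apart here because of how the conditions are built. TMS alone, paired and unpaired all contain active rTMS; taVNS alone does not. Participants are chosen for responding to rTMS, and the plan itself expects taVNS alone to be weaker. On the plan's own expectations the ANOVA null hypothesis is false even if pairing adds nothing.

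Two things are at stake. A significant F could be taken as support for pairing when it reflects only the presence or absence of rTMS. And a null result for paired against TMS alone could be read against an 80% figure that belongs to a different test. With no multiplicity rule, three unadjusted tests at 5% would also give at least one false positive in about 13% of trials when nothing differs (simulated; 1 − 0.95³ = 14.3% if the tests were independent).

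**Working it through.** **Inputs from the documents.** n = 24 and four conditions (Study Design); effect 0.06, alpha 0.05 and power 80% (Power Calculation).

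**Assumptions, because the documents give no value.** Between-condition correlation ρ from 0.3 to 0.7, equal for all pairs; one MEP-change value per visit; no dropout; the patterns of means shown below.

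**1. Effect size.** Reading 0.06 as partial eta-squared, f² = 0.06/0.94 = 0.0638 and f = 0.253.

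**2. The plan's 80%.** For a repeated-measures F test, λ = n × m × f²/(1 − ρ), with m − 1 = 3 and (m − 1)(n − 1) = 69 degrees of freedom. At ρ = 0.5, λ = 24 × 4 × 0.0638/0.5 = 12.26.

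| ρ | λ | Power of F |
|---|---|---|
| 0.3 | 8.75 | 67.0% |
| 0.5 | 12.26 | 82.6% |
| 0.7 | 20.43 | 97.0% |

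Exactly 80% is reached at ρ = 0.47. Other combinations also reach it: 20 participants at ρ = 0.56, five or six levels at ρ = 0.39 or 0.32, or a sphericity epsilon of 0.75 at ρ = 0.57. If 0.06 were already expressed on within-subject error, λ = 0.0638 × 69 = 4.40 and power would be 37%. So the 80% is plausible, but the plan does not state the inputs needed to confirm it.

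**3. No pairing benefit.** Take means 0, 1, 1, 1 for taVNS alone, TMS alone, unpaired and paired, scaled to f = 0.253. The power of F depends on the means only through f, so it is again 67.0%, 82.6% and 97.0%. In 40,000 simulated trials per value of ρ, F was significant without a significant paired > TMS alone contrast in 65%, 80% and 95% of trials. That contrast itself was significant in the favourable direction in about 2.5%, its false-positive rate.

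**4. Power for the pairing contrasts when there is a benefit.** Scale each pattern to the same f, set dz = difference/√(2(1 − ρ)), and use a two-sided paired t-test with 23 degrees of freedom. At ρ = 0.5 the divisor is 1.

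| Means (taVNS, TMS, unpaired, paired) | Nearest comparator to paired | dz | Power |
|---|---|---|---|
| 0, 1, 2, 3 | unpaired | 0.226 | 19% |
| 0, 1, 1, 2 | TMS alone and unpaired | 0.357 | 39% |
| 0, 1, 1, 3 | TMS alone and unpaired | 0.464 | 59% |
| 0, 0, 0, 1 | all three | 0.583 | 78% |

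All four patterns give F the same 82.6% power. Over ρ from 0.3 to 0.7 the contrast power runs from 15% to 94%.

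**5. What 24 participants can detect on one contrast.** Solving the paired t-test for 80% power gives dz = 0.597 with 24 completers and 0.660 with 20 (20 is an illustration). At 0.05/3 the values are 0.705 and 0.784. A mixed model with pooled error is slightly more favourable (0.58 with 69 degrees of freedom, before any period term), so these figures are mildly conservative.

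**The case against.** The study is described as a mechanistic pilot in healthy volunteers. The power paragraph sits under Data Management, does not say that the ANOVA is the only analysis, and does not claim 80% for Aim 2. It states a within-subject design, so a repeated-measures ANOVA is the fair reading, and on that reading at ρ = 0.5 the claim holds with 82.6%. The endpoint and design figures are not available in the text reviewed.

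Much of this stands, and it rules out several stronger readings that a reader might infer:

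- That the 80% is false, or holds under only one set of inputs. Step 2 shows several combinations that reach it.
- That the ANOVA treats 96 values as independent, or that 0.06 is an unsquared eta. The first contradicts the stated within-subject design; the second takes loose wording literally.
- That the unpaired condition is undefined. Its descriptions do conflict. The bracket in Aim 2 names taVNS twice. Pairing taVNS with TMS (section 3.0) describes unpaired delivery as independent, while Stimulation Parameters describes it as concurrent. Study Design lists six labels for four conditions. But the figures cited there are not shown, so the text establishes only that the descriptions need reconciling.

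What the objection does not do is supply a test for Aim 2. Follow-up comparisons may be intended, but none is written, and pilot status does not change which question the stated 80% answers.

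**Conclusion.** The concern holds as an omission with a practical consequence, and it should be fixed. The one test named and powered does not answer Aim 2, and on the plan's own expectations it is likely to be significant whether or not pairing helps. The percentages rest on the assumed correlations and patterns of means; the structural point does not.

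A reader might go on to infer that 24 participants are too few. The documents do not support that. The contrast power of 19% to 78% at ρ = 0.5 reflects the pattern of means chosen, and the plan gives no expected difference for any pairing contrast against which to judge the sample size. The finding is that the 80% does not carry over to Aim 2.

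**What to change.** In the Power Calculation paragraph, state that Aim 2 is tested by three prespecified two-sided within-subject contrasts on a single MEP-change summary fixed in advance. Use a linear mixed model with condition and visit (period) as fixed effects and participant as a random effect; the period term is needed because this is a counterbalanced four-visit crossover. Test at 0.05 in the order in which Aim 2 gives them: paired vs TMS alone, paired vs taVNS alone, paired vs unpaired. Stop at the first non-significant result and claim each contrast separately. Holm is an acceptable alternative.

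Restate power along these lines: 24 completers give 80% power for a within-subject standardised difference of 0.60 on paired vs TMS alone (0.66 with 20 completers); power for later contrasts is lower because each depends on the earlier ones. With Holm, quote 0.70 and 0.78 instead, as conservative figures. Keep the 80% ANOVA figure only as secondary, with its sample size, number of levels, correlation and effect-size definition.

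Separately, reconcile the descriptions of the unpaired condition in sections 1.0, 3.0 and 10.0. This review does not say which delivery schedule is right.

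The cost is a less favourable power statement and lower power for the last contrast. At ρ = 0.5, under patterns 0,1,2,3 / 0,1,1,2 / 0,1,1,3, paired vs unpaired would be claimed in about 15% / 22% / 41% of trials, against 19% / 39% / 59% if tested alone. Paired vs taVNS alone would be claimed in 54% / 38% / 56%, against 89% / 92% / 90% alone. Holm keeps 78% / 82% / 81% for that contrast, but lowers paired vs TMS alone from 56% / 39% / 58% to 44% / 31% / 50%. No extra participants or visits are needed.

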### Estimated Difficulties, Limitations and Time Frames

*Estimated Difficulties.* Healthy control MEP studies have been conducted in our laboratory for over 20 years – with minimal difficulty. For this particular study the estimated difficulty will likely be minimizing dropout over 5 experimental visits.

*Limitations.* There are two potential limitations with these studies. The first is tolerability of electrical nerve stimulation of the tragus and earlobe. Although we do not anticipate any issues, drop-out may be an issue due to discomfort of the stimulation.

*Estimated Time Frames.* We plan on completing this study over the next 6-8 months.

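### The power paragraph names a one-way ANOVA for a within-subject design; taken literally this is the wrong test, and the stated 80% is recovered only with a repeated-measures test and inputs the plan does not give

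*Combined protocol and SAP*

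**What the plan says.** The Power Calculation in section 11.0 opens: "Our proposal utilizes a within-subject design, in which each subject will be their own control". It takes its effect from earlier work: "Using the low end of a range of effect sizes (derived from 0.06 partial eta) from prior excitatory TMS/MEP studies". It then claims sufficient power to detect a change in MEP magnitude, "using a one-way ANOVA at 80% power and 5% significance level". The paragraph gives no sample size, number of factor levels, between-visit correlation or sphericity assumption.

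The design is set out elsewhere. Section 1.0 describes 24 healthy people "in a 4 visit, randomized, sham controlled, counterbalanced study". The Study Design part of section 10.0 says the trial will "subsequently enroll a total of 24 healthy participants" from a prescreened group ("We will enroll 40 healthy individuals into a motor excitability prescreening visit"). On conditions it says "Participants will then receive 20 minutes of one of four different stimulation conditions", although the bracket that follows lists six labels.

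On losses, section 10.0 (Estimated Difficulties, Limitations and Time Frames) says "drop-out may be an issue due to discomfort of the stimulation". Section 3.0 (Motor-Evoked Potentials) withdraws a participant whose baseline stays too variable. No replacement rule is given, and the plan does not say whether 24 means starters or completers.

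**The concern.** The sentence in section 11.0 is the only place where a statistical test is named, so it also serves as the analysis plan. A one-way ANOVA without a participant term treats the four measurements on each person as if they came from four different people. When measurements on the same person are positively correlated, this leaves the between-person variation in the error term and gives up the benefit of the crossover. The test becomes very conservative and loses power.

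The choice of test changes the result obtained from the same data, and it decides whether the stated 80% can hold. Even with the right test, the 80% depends on a correlation, a sphericity assumption and an effect-size scale that the paragraph does not state.

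**Working it through.** **Inputs from the plan.** n = 24 and four conditions (sections 1.0 and 10.0); alpha 0.05; effect 0.06 (section 11.0).

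**Inputs assumed.** Between-visit correlation ρ (0.3 to 0.6 shown), sphericity ε (1, 0.9 and 0.75), and the scale of the 0.06. Read as an eta-squared on the total-variance scale, f² = 0.06/0.94 = 0.0638 and f = 0.2526.

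**1. Reproducing the 80% with a repeated-measures test.** λ = f² × n × 4 × ε/(1 − ρ), with df 3ε and 3(n − 1)ε. At n = 24, ρ = 0.5 and ε = 1, λ = 0.0638 × 96/0.5 = 12.26 on 3 and 69 df, which gives power 82.6%. The smallest correlation that gives 80% at n = 24 is 0.47.

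**2. Sensitivity of that figure.**

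| Assumption varied (n = 24 unless stated) | Power |
|---|---|
| ρ = 0.3 / 0.4 / 0.5 / 0.6, ε = 1 | 67.0% / 74.4% / 82.6% / 90.6% |
| ρ = 0.5, ε = 0.9 / 0.75 | 79.4% / 73.5% |
| ρ = 0.5, ε = 1, with 23 / 22 / 21 completers | 80.7% / 78.6% / 76.3% |
| 0.06 as partial eta-squared on the within-subject error | 37.2% |

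For the last row, λ = f² × (n − 1) × 3 = 0.0638 × 69 = 4.40, with no further gain from ρ because the scale already contains it. On that scale 80% needs 60 participants. Put the other way, the 82.6% corresponds to a within-error partial eta-squared of 12.26/(12.26 + 69) = 0.15, not 0.06.

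**3. The test as literally named, on this design.** With participant left out, the expected error mean square is the whole variance σ², against (1 − ρ)σ² in the repeated-measures test, so the one-way F is about (1 − ρ) times the repeated-measures F. At ρ = 0.5 the repeated-measures critical value F(3, 69) = 2.737 (p = 0.05) becomes about 1.369 on 3 and 92 df, which is p = 0.257.

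Simulation of 24 people under four conditions, the same data analysed both ways:

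| ρ | One-way: power | One-way: true type I error | Repeated measures: power | Repeated measures: type I error |
|---|---|---|---|---|
| 0.3 | about 46% | about 1.2% | about 67% | about 5% |
| 0.5 | about 41 to 42% | about 0.3% | about 83% | about 5% |
| 0.6 | about 39% | below 0.1% | about 91% | about 5% |

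**4. The independent-groups formula, for comparison.** With 96 different people, 24 per condition, λ = 0.0638 × 96 = 6.13 on 3 and 92 df and power is 50.9%; 80% needs 44 per condition. This is a different situation from step 3: it describes 96 people, not 24 people measured four times.

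**The case against.** The strongest reply is that one-way counts factors and does not assert independence. A one-factor ANOVA can be a repeated-measures one, and the paragraph begins by saying that each person is their own control. This stands to the extent that the wording is probably shorthand, so calling it an outright contradiction would go too far. The losses in step 3 occur only if an analyst ignores that opening sentence. But no other text names the paired test, and the literal reading gives a different p-value from the same data.

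A second reply is that a correlation of 0.5 is this review's assumption. It is, which is why a range is shown. The plan's 80% also needs a correlation, and none is given.

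Two stronger readings are tempting. A reader might infer that 24 is too few. The documents do not show this, because under step 1 the 80% is attainable. A reader might instead infer that the 80% is right and only the test name needs correcting. The documents do not show that either. The scale of the 0.06 is not stated, and a modest departure from sphericity (ε = 0.9) already takes power just below 80%.

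On attrition, the plan gives no loss rate, so a claim that drop-out will pull power below 80% would rest on assumed rates. A count of completers also presumes that incomplete participants are discarded, which a mixed model would not do. The withdrawal for an unstable baseline is not tied to a visit, so some of it may occur at prescreening, before the 24 are chosen.

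**Conclusion.** Wrong as written; severity minor. The only named test, taken literally, does not fit the design. With 24 participants, f = 0.2526 and an assumed correlation of 0.5, it would run at about 0.3% true type I error and about 41 to 42% power. The stated 80% belongs to a repeated-measures test and holds only under a joint set of unstated conditions: total-variance scale for the 0.06, correlation of at least 0.47, sphericity, four levels, and 23 to 24 completers (23 at correlation 0.5). Within the ranges examined, repeated-measures power runs from about 37% to 91%, so the 80% can be neither confirmed nor rejected from the documents. All of these figures are for the omnibus test of condition and say nothing about power for the Aim 2 contrasts. The study is a pilot in healthy people, which keeps the severity low.

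**What to change.** In section 11.0, replace the one-way ANOVA with one of two tests:

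- a one-factor repeated-measures ANOVA with a sphericity correction; or
- a linear mixed model with a participant random effect, which also keeps the completed visits of people who drop out.

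Restate the power for the chosen test with the inputs actually used: effect-size scale, between-visit correlation, epsilon, four condition levels and number of completers. State that it is omnibus power and not the power of the Aim 2 contrasts. The 82.6% above should not be printed unless the sponsor confirms the total-variance scale and the other inputs behind it. If the sponsor's inputs do not support 80%, print the lower figure.

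Secondary and optional: say that 24 means completers, or report the power for the number who complete. If people lost are replaced from the prescreened responders, each replacement should take the vacated sequence so that the counterbalancing is kept.

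The cost is one paragraph of wording. The test and inputs can be corrected without changing the design or the planned 24. Replacement depends on how many of the 40 prescreened people respond, which the plan does not state: 24 starters already need 24/40 = 60%.

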## **12.0 Provisions to Monitor the Data to Ensure the Safety of Subjects**

There are three areas in which safeguards to protect subjects from undue risk require discussion. These include: (1) procedures used to obtain informed consent, (2) procedures used to ensure confidentiality of the subject data, and (3) procedures used to minimize possible risks associated with the laboratory procedures. Regarding informed consent, participants are fully advised on the research procedures to be used, the amount of time required of them, the possible risks and benefits of the procedures, their right to refuse participation in the study without prejudice, their right to terminate participation at any moment without prejudice, and the name and telephone number of the principal investigator. All subjects will be required to have capacity to consent. Regarding confidentiality, subjects are informed that the information they provide will be kept strictly confidential, with access limited to the research staff.

Participation in the study will be treated as confidential, as will all records. The identity of subjects will be protected with alphanumeric codes. All data will be kept in locked file cabinets file cabinets or on secure servers designed for use and access by Brain Stimulation Lab members only.

An independent Data Safety Monitoring Board (DSMB) will be formed to advise the study investigators. The DSMB will review and evaluate accumulated study data to ensure safety. They also will make recommendations concerning continuation, modification, or termination of any of the taVNS/TMS studies. It will be composed of [name], MUSC psychiatrist with expertise in transcranial magnetic stimulation (TMS); [name], MUSC associate professor and assistant provost with extensive VNS, TMS, and tDCS experience; [name], MUSC Psychiatrist with expertise in TMS.

The DSMB will review all the data from the study in order to ensure safety of participants. We do not anticipate any adverse events to occur in this study, however the experienced research team has a long standing record of recording and reporting unanticipated adverse events to the IRB. We will report any adverse event within 48 hours to the IRB and to the DSMB.

